5 LIST OF POSSIBLE ABBREVIATIONS

Ab	Antibody
ABC	Automated Blood Count
ACD	Acid Citrate Dextrose
ACLS	Advanced Cardiac Life Support
ACTH	Adrenocorticotrophic Hormone
APAAP	Alkaline Phosphatase Antialkaline Phosphatase Complex
ALT	Autologous Lymphocyte Transfer
AST	Aspartate Aminotransferase
ASTCT	American Society for Transplantation and Cellular Therapy
AT	Ambient Temperature
β -HCG	Beta-Human Chorionic Gonadotropin
BTSC	Brain Tumor Stem Cells
Ca ⁺⁺	Calcium
cDNA	Complimentary Deoxyribonucleic Acid
CFA	Complete Freund's Adjuvant
CFC	Cytokine Flow Cytometry
CLIA	Clinical Laboratory Improvement Act
CMP	Comprehensive Metabolic Panel
CMV	Cytomegalovirus
CNC	Clinical Neurologic Change
CNS	Central Nervous System
Con-A	Concanavalin A
CPC	Cancer Protocol Committee
CRS	Cytokine Release Syndrome
CT	Computed Tomography
CTL	Cytotoxic T-Lymphocyte
DC	Dendritic Cell
DI	Dose Intensified
DLT	Dose Limiting Toxicity
DTH	Delayed-type Hypersensitivity
EAE	Experimental Autoimmune Encephalomyelitis
EBRT	External Beam Radiation Therapy
ELISA	Enzyme-Linked ImmunoSorbent Assay
ELISPOT	Enzyme-linked Immunospot
EGFR	Epidermal Growth Factor Receptor
EGFRvIII-KLH	EGFRvIII conjugated to Keyhole Limpet Hemocyanin
FACS	Fluorescence Activated Cell Sorting
FDA	Federal Drug Administration
FEV	Forced Expiratory Volume
gB	Glycoprotein B
GBM	Glioblastoma
GM-CSF	Granulocyte Macrophage Colony Stimulating Factor
HIV	Human Immunodeficiency Virus
HLA	Human Leukocyte Antigen
I.D.	Intradermal
IFN- γ	Interferon-gamma

IHC	Immunohistochemistry
IL-4	Interleukin-4
IL-12	Interleukin-12
IL-13	Interleukin-13
IRB	Institutional Review Board
KLH	Keyhole Limpet Hemocyanin
KPS	Karnofsky Performance Status
MAb	Monoclonal Antibody
MG	Malignant Glioma
MHC	Major Histocompatibility Complex
MRI	Magnetic Resonance Imaging
mRNA	Messenger Ribonucleic Acid
MTD	Maximally Tolerated Dose
NA	Non-adherent
NCI CTC	National Cancer Institute Common Toxicity Criteria
NIH	National Institutes of Health
NK	Natural Killer
OS	Overall Survival
PBMC	Peripheral Blood Mononuclear Cells
PD	Progressive Disease
PHA	Phytohemagglutinin
PFS	Progression Free Survival
PI	Principle Investigator
PT	Prothrombin Time
PTT	Partial Thromboplastin Time
RANO	Revised Assessment in Neuro-Oncology
RNA	Ribonucleic Acid
RT	Radiation Therapy
RT-PCR	Reverse Transcriptase Polymerase Chain Reaction
SAE	Severe Adverse Event
SLPs	Synthetic Long Peptides
SOC	Standard of Care or Safety Oversight Committee
SPORE	Specialized Program of Research Excellence
TCR	T-cell Receptor
TGF- β	Transforming Growth Factor- β
TMZ	Temozolomide
TNF- α	Tumor Necrosis Factor- α
T _{Regs}	Regulatory T-cells
TTTP	Time to Progression
TTRNA	Total Tumor mRNA
WHO	World Health Organization
XRT	External Beam Radiation Therapy
XRT/TMZ	Temozolomide During Concomitant Radiation Therapy

6 DEFINITION OF TERMS

Term	Definition
Date of diagnosis	Earliest confirmation by radiographic or histologic examination
Date of randomization	Date TMZ regimen is assigned.
Date of progression	Earliest date of surgical confirmation of disease progression. Where surgery is not feasible, earliest date of radiographic confirmation of progression.
Enrolled patient	Patient who signs the informed consent form and meets all eligibility criteria.

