8.2.3 Exploratory Objectives

- To quantitate the immune response to the PEP-CMV vaccine by pp65 ELISPOT.
- To determine the quality of the immune response by polyfunctional flow cytometry using the pp65 peptide in PEP-CMV.
- To evaluate if Treg levels remain the same or decrease after vaccination.
- Identify if any HLA haplotypes respond better to the vaccine.
- To characterize immunologic cell infiltrate in tumors at the time of disease progression/recurrence.
- To describe PFS and OS within the 2 arms.
- To estimate radiographic response rate to PEP-CMV in the subset of patients with residual disease.

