Patients who receive more than 1 cycle of TMZ will be vaccinated in conjunction with each **subsequent** 28-day TMZ cycle for a total of 6 to 12 cycles of TMZ after RT followed by further vaccination up to 20 vaccines. Patients who receive only 1 cycle of TMZ will be vaccinated on a 28-day cycle with up to 20 vaccines. All cycles, with or without TMZ, may be given every 4 (+ 2) weeks, in order to adjust for slight delays on startup of each 28-day cycle, and the total number of cycles are given at the discretion of the treating oncologist. During vaccine (+/- TMZ) cycles, vaccinations will occur on day 23 (-1 day, + 2 days) of each cycle for each arm: (Arm 1) standard TMZ (150-200 mg/m²/day on days 1-5 of each 28-day cycle), or (Arm 2) dose-intensified TMZ (75-100 mg/m²/day on days 1-21 of each 28-day cycle). All vaccines will be given i.d. approximately 10 cm below the inguinal ligament bilaterally. A target of six cycles with a maximum of twelve cycles of TMZ may be given to patients enrolled prior to approval of protocol version 20181218 and those with MGMT/inconclusive methylation status if enrolled after approval of protocol version 20181218, at the discretion of the treating neuro-oncologist. After the completion of a patient's TMZ cycles, vaccines will continue to be administered every 4 (+ 2) weeks for a maximum of 20 vaccines (unless tumor progression occurs).

Patients will be imaged with contrast-enhanced MRI after vaccine 3 (at cycle 2 initiation visit) and then approximately every 8 weeks [every 2 cycles thereafter (i.e., end of cycles 3, 5, 7, 9, 11)]. RANO criteria [111] will be used for assessment of pseudoprogression and patients demonstrating definitive progression will be removed from study. Any patient removed prior to immune monitoring post vaccine 3 will be replaced for immunologic endpoints. Clinical endpoint comparisons will be made amongst patients randomized to adjuvant TMZ treatment arms who have received at least one vaccine.

Blood for immune monitoring will be obtained:

- Prior to Td pre-conditioning
- During vaccines 1 and 2 (just prior to Component A, 1 and 2 hours after Component A)
- Prior to vaccine 3
- After vaccine 3 (within 2 weeks of vaccine 3 [+ 3 days])
- Prior to vaccines 4 and 6
- At tumor progression (if feasible)

Patients seen by the Duke neuro-oncology team between these vaccine visits may have blood drawn for immune monitoring at the discretion of the study team.

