As part of standard care for these patients, upon tumor progression, participants may undergo stereotactic biopsy or resection. As this is not a research procedure, consent will be obtained separately. Patients who have this procedure done here in the Duke University Health System may be approached to participate in the Duke Brain Tumor Center Biorepository study (Pro00007434). Tissue obtained from patients who consented to the Duke Brain Tumor Center Biorepository will be used to assess immunologic cell infiltration, antigen expression, and biomarkers for immunologic response.

Study Drug Safety Arm (added 5/16/17 following safety events that occurred on 4/5/17, not applicable for patients enrolled on protocol version 6/12/18 or later)

Definition of Study Drug Safety Arm:

The purpose of this 6 patient safety arm is to investigate which component or combination of components of the PEP-CMV vaccine (PEP-CMV is administered as two components: Component A and Component B) results in a hypersensitivity reaction, similar to that seen in the first 3 patients treated with the vaccine. Serious Adverse Events for the first 3 patients receiving study drug vaccine were submitted to FDA and the IRB on 4/10/17. These patients experienced rapid onset (within 2 hours of vaccine) of a combination of the following symptoms: nausea, vomiting, diarrhea, chills, fever, myalgias, dyspnea, generalized muscle weakness, back pain, and cough. We believe that the combination of the vaccine components administered at the same time resulted in this intense hypersensitivity reaction and by administering the components with a delay, we may alleviate the severity of these reactions. Additionally, by administering the components separately, we can determine if it's an individual component or a combination of the components that results in the reaction. After we determine which component or combination of components is related to the hypersensitivity reaction, we will put the study on a temporary hold and investigate how we can modify the study drug or administration procedure in order to reduce the occurrence of these reactions.

Rationale of Study Drug Safety Arm:

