11.10 Early Withdrawal of Subject(s)

11.10.1 Criteria for Early Withdrawal

Subjects may voluntarily withdraw from the study at any time. The PI may also withdraw a subject from the study at any time based on his/her discretion. Reasons for withdrawal may include at the PI’s discretion may include, but are not limited to, the following:

- Progressive disease as documented by MRI or physical examination at any time after the initiation of immunotherapy
- Development of unacceptable toxicity
- Pregnancy
- Patients requiring an increase in corticosteroids, with the exception of nasal or inhaled steroid, such that at the time of first vaccination they require a dose above immune suppressive levels, will be removed from the study and replaced. For the purposes of this study, immune suppressive dose will be defined as ≤4 mg of dexamethasone / day or equivalent. Once vaccinations have been initiated, if patients subsequently require increased steroids, they will still be permitted to remain on the study, but every effort will be made to minimize steroid requirements
- Abnormal laboratory values
- Upon request of the subject
- If, in the investigator’s medical judgment, further participation would be injurious to the subject’s health or wellbeing
- Development of intolerable symptoms
- Protocol deviation
- Administrative reasons, such as a major violation of the clinical trial protocol
- Non-compliance of the subject
- Clinical decline
- Allergic or hypersensitivity reaction to Td vaccine
- Allergic or hypersensitivity reaction to PEP-CMV
- Failure to tolerate TMZ therapy for any reason
- Development of any of the following co-morbidities:
 - Unstable angina and/or congestive heart failure requiring hospitalization.

- Transmural myocardial infarction within the last 6 months.
- Hepatic insufficiency resulting in clinical jaundice and/or coagulation defects; note, however, that laboratory tests for liver function and coagulation parameters are not required for entry into this protocol.
- Acquired Immune Deficiency Syndrome (AIDS) based upon current CDC definition; note, however, that HIV testing is not required for entry into this protocol. The need to exclude patients with AIDS from this protocol is necessary because the treatments involved in this protocol may be significantly immunosuppressive.
- Major medical illnesses or psychiatric impairments that in the investigator's opinion will prevent administration or completion of protocol therapy.

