12.8 Measurement of Radiographic Response

Patients with newly-diagnosed GBM will be imaged by MRI as per standard of care for eligibility and baseline measurements, to assess progression after vaccine 3 (at the TMZ cycle 2 initiation visit, if applicable) and then approximately every 8 weeks (or every other vaccine), coinciding with every 2 cycles of TMZ, if applicable (i.e., end of cycles 3, 5, 7, 9, 11). Although the purpose of this study is not to detect tumor responses, any evidence of

tumor response will be determined according to the Duke PRTBTC SOP (see [Appendix D – SOPs and FORMs](#)). RANO criteria [111] will be used for overall assessment of tumor response and pseudoprogression. Tumor progression will need to be documented histologically, unless there are clinical contraindications, to exclude inflammatory responses presenting as radiographic or clinical changes, which could indicate potentially toxic or therapeutic responses and not tumor progression. If tissue is obtained, it will be used to confirm tumor progression histologically and to assess immunologic cell infiltration and antigen escape using IHC. Upon progression, patients will be taken off study treatment and may be treated on other therapies as directed by the treating oncologist.

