15.4.4 Other Exploratory Analyses

Progression-Free Survival and Overall Survival: The Kaplan-Meier estimator will be used to describe the progression-free survival (PFS) and overall survival (OS) experience of patients in each treatment group. These analyses will focus on those patients who have received at least 3 vaccines. PFS is defined as the time between the third vaccine and first documentation of death or disease progression/recurrence. Patients remaining alive without disease progression will have PFS censored at their last follow-up. OS is defined as time between the third vaccine and death. It should be noted that these analyses will focus on only those patients who received Component A alone as we have with other analyses. Additional analyses will describe OS and PFS from randomization.

Radiographic Response: Among the subset of patients with residual disease, the proportion of patients with radiographic response will be estimated with 95% confidence interval.

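### Section 6 dates progression at surgery and falls back on imaging only where surgery is not feasible, so an operated patient's PFS includes the wait for surgery and some patients have no defined progression date

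*Combined protocol and SAP*

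**What the plan says.** Section 6 (Definition of Terms) gives the date of progression as "Earliest date of surgical confirmation of disease progression. Where surgery is not feasible, earliest date of radiographic confirmation of progression".

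Section 15.4.4 defines the endpoint without citing Section 6: "PFS is defined as the time between the third vaccine and first documentation of death or disease progression/recurrence". It does not say what kind of documentation counts.

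Other sections bear on which date is meant:

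- Section 12.8 asks for histology: "Tumor progression will need to be documented histologically, unless there are clinical contraindications, to exclude inflammatory responses presenting as radiographic or clinical changes".
- Section 11.1 applies RANO criteria and states that "patients demonstrating definitive progression will be removed from study".
- Section 11.10.1 lists among possible reasons for withdrawal "Progressive disease as documented by MRI or physical examination at any time after the initiation of immunotherapy".
- Section 11.1 treats surgery as optional standard care that comes after progression: "upon tumor progression, participants may undergo stereotactic biopsy or resection". No time window is given.

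The objective in Section 8.2.3 is exploratory: "To describe PFS and OS within the 2 arms".

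**The concern.** One event has two clocks, and surgical status decides which applies. Surgery follows the imaging or clinical change that prompts it, so an operated patient's event date is later than the date of that change by a scheduling interval. A patient taken off study on MRI and operated on some weeks later would, under Section 6, count as progression-free in between. Two analysts working from Sections 6 and 15.4.4 could enter different dates for that patient.

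The rule also leaves a gap. The radiographic date is available only where surgery is infeasible, yet surgery is optional. Where it could be done but is not, neither branch supplies a date. Read literally, such a patient would run on to death or be censored at last follow-up.

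At stake are the Kaplan-Meier PFS curves by arm and any proportional hazards model of PFS on HLA haplotype (Section 15.4.3). Section 15.4.4 plans no between-arm test of PFS. However, Section 11.1 speaks of clinical endpoint comparisons, and Section 8.1 expects PFS and OS to be informative about the two temozolomide regimens. The curves are therefore likely to be read side by side.

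**Working it through.** The plan states no PFS sample size, event count, reoperation share or imaging-to-surgery interval, so there is no figure of its own to reproduce. The check has two parts.

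**Which date applies.** The same patient is followed through the text.

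| Situation | Date under Section 6 | Date if 15.4.4 means the first MRI or clinical evidence |
|---|---|---|
| MRI shows progression, surgery later confirms it | Surgery | MRI |
| MRI shows progression, surgery not feasible | MRI | MRI |
| MRI shows progression, surgery feasible but not done | None defined | MRI |

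If 15.4.4 is instead read with Section 12.8, first documentation means histology wherever tissue can be obtained. The first row then agrees with Section 6, but the third row still has no date.

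**Size of the added time.** Inputs from the documents: PFS of 6.7 months (historical controls) and 29.2 months (earlier dendritic-cell trial), both in Section 9.7; 15.4 months in the Section 7.1 abstract; a target of 13 evaluable patients per arm in Section 15.1. Assumptions, not in the documents: a delay of 4 to 8 weeks from imaging to surgery, and half of patients operated on.

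Relative lengthening for an operated patient = delay / PFS in weeks, with weeks = months × 52.18/12.

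- 6.7 months = 29.1 weeks: 4/29.1 = 14%, 8/29.1 = 27%.
- 15.4 months = 67.0 weeks: 4/67.0 = 6%, 8/67.0 = 12%.
- 29.2 months = 127.0 weeks: 4/127.0 = 3%, 8/127.0 = 6%.

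In absolute terms an operated patient gains 0.92 months for 4 weeks and 1.84 months for 8 weeks. A 1-week delay would add 0.23 months.

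Rise in mean PFS for a group = share operated × delay: 0.5 × 4 = 2 weeks (0.46 months) and 0.5 × 8 = 4 weeks (0.92 months).

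A simulation with exponential PFS at the three medians, adding the delay to operated patients only, gives nearly the same shift in the median whatever the true median. With half operated it is 0.46-0.47 months for 4 weeks and 0.93-0.97 months for 8 weeks. At 25% operated the shifts are 0.22-0.24 and 0.46-0.49 months; at 75% they are 0.69-0.70 and 1.39-1.41 months.

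**Arm contrast.** With equal delay in both arms, the spurious difference in mean PFS = delay × difference in share operated. If 13 patients per arm all progress and the true share is one half in each, the standard deviation of the difference in shares is √(2 × 0.5 × 0.5/13) = 0.196. A one-standard-deviation imbalance therefore gives 0.196 × 4 = 0.8 weeks to 0.196 × 8 = 1.6 weeks. A 25% versus 75% split, with equal true PFS at a median of 6.7 months, gives a spurious median difference of 0.46 months (4 weeks) or 0.92 months (8 weeks). That split is 0.50/0.196 = 2.6 standard deviations, so it is an upper illustration and not an expected result.

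**The case against.** A reader might infer that Section 6 contradicts Section 15.4.4. The documents do not establish that. Section 15.4.4 leaves the type of documentation open, and Section 12.8 calls for histology unless contraindicated; read together, they can agree with Section 6. Section 11.10.1 is a list of possible reasons for withdrawal at the investigator's discretion and does not set an event date. The RANO rule in Section 11.1 likewise governs removal from study. Both show that the plan recognises progression on MRI or examination; neither fixes the PFS clock.

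A reader might also infer that operated patients will show longer PFS than unoperated patients for reasons unrelated to disease. That goes too far. Section 12.8 gives a disease-based reason for histology, namely to exclude inflammatory change, and Sections 11.3 and 11.5.2 show that this is a real issue here. Feasibility of surgery also depends on the disease. Only the waiting time is extraneous, and the lengthening is relative to the same patient's own imaging date.

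Third, the rule is the same in both arms, PFS is exploratory and descriptive, and the HLA model is conditional. No primary endpoint, sample size or safety rule is affected. This stands and limits the importance of the point. The origin of the 6.7-month figure is also not stated, whereas Section 15.4.4 starts PFS at the third vaccine, so the percentages are only indicative.

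None of this removes the two clocks or the missing date. The need to exclude inflammatory change justifies requiring confirmation; it does not require the event to be dated at the confirming procedure.

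**Conclusion.** The point holds as a defect in an event-date definition, of minor weight. Section 6 adds the wait for surgery to an operated patient's PFS and gives no date when feasible surgery is not done. Section 15.4.4 does not settle which date to use.

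The size rests on an assumed delay and an assumed share operated. The range for an operated patient is wide, about 3% to 27%, because it depends on which of the three quoted PFS figures is the reference. The absolute shift is steadier, at 2 to 4 weeks in the mean if half are operated on. Distortion between arms needs a difference in reoperation share or delay. The documents give no reason to expect a systematic one, but with 13 per arm it can arise by chance.

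**What to change.** For the PFS analysis, date progression in every patient at the first MRI or clinical examination that showed the change later confirmed as progression. Confirmation is by histology where tissue is obtained, and otherwise by the RANO assessment the plan already uses. Histology then confirms or refutes the event but does not set its date. State this rule once and cross-reference it in Sections 6, 12.8 and 15.4.4. Report surgery-dated PFS as a sensitivity analysis. The change concerns only the analysis date and leaves the rules for withdrawal and for obtaining tissue as they are.

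The cost is one definition and its cross-references. PFS becomes slightly shorter. Both the imaging (or examination) date and the surgery date must be kept; Section 11.9 says only that progression and survival data are recorded, so the case report form should be checked for both.

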7 ABSTRACT AND STUDY SCHEMA

7.1 Abstract

Despite aggressive, computer-guided surgery, high-dose focused radiation, and toxic, multimechanistic chemotherapy, MGs remain almost universally fatal. Moreover, these inherently non-specific conventional treatments incapacitate patients as a result of damage to surrounding normal brain and systemic tissues[1]. The inherent biologic specificity of immunotherapy, however, offers the prospect of targeting neoplastic cells more precisely.

The recent discovery that GBMs, but not surrounding normal brain tissue, serve as a refuge for CMV reactivation provide an unparalleled opportunity to subvert, as tumor-specific antigens, the highly immunogenic viral proteins expressed by human CMV. The immunologic responses to CMV have been well-characterized and the immunodominant viral protein pp65 is highly-conserved. Finally, CMV-specific immunotherapy has been previously shown in humans to be safe and efficacious in combating CMV related disease within the CNS, and antitumor immunotherapy targeting viral proteins in human CNS tumors associated with Epstein-Barr virus (EBV), another *Herpesvirus*, have been curative[2-7]. Similarly, vaccinations directed against the highly immunogenic antigens of human papilloma virus have been shown to reduce the incidence of cervical intraepithelial neoplasia in a prospective, randomized, double-blind trial[8].

Chemotherapeutic agents frequently used in cancer therapy, however, often induce a profound lymphopenia that may inhibit even the most potent anti-tumor immune responses. TMZ, a methylating chemotherapeutic agent, has recently shown efficacy in some patients with newly diagnosed GBM who are MGMT methylated, and TMZ is now frequently given to these patients during and after RT. Therapeutic TMZ, however, also induces a profound lymphopenia. ALT after TMZ therapy may provide a source of T-cells that remain receptive to vaccination in this context while potentially protecting the patient from opportunistic infections as well. In addition, the homeostatic proliferation of T-cells that is triggered in response to lymphopenia may even potentiate anti-tumor vaccine or adoptive T-cell responses [9].

[figure not shown]
Our recent clinical trial with DC-based vaccination targeting the immunodominant CMV antigen pp65 has produced immunologic responses in patients with GBM undergoing standard of care TMZ along with encouraging PFS (15.4 months, CI₉₅: 10.0, 27.8). In order to advance vaccines targeting CMV in GBM, we have developed a CMV-specific peptide (PEP-CMV). PEP-CMV is a vaccine comprised of two components (referred to as Component A and Component B). Component A, pp65 synthetic long peptide (SLP) is a single peptide from human CMV matrix protein pp65SLP. Component B consists of a neutralizing antibody epitope from human CMV glycoprotein B conjugated to KLH (gB-KLH). Component A will be administered as a stable water:oil emulsion in Montanide ISA 51 (Incomplete Freund's Adjuvant). The gB-KLH conjugate (referred to as Component B) will be administered in aqueous solution with 150 µg of GM-CSF. Due to insufficient manufacturing of Component B followed by safety events in a subset of patients who received Component B, no patients will receive Component B as of 20190130.

Our preliminary data demonstrating the capacity to increase DC migration to VDLNs via Td pre-conditioning of the vaccine site offer potential therapeutic interventions whereby we can enhance the immunologic responses to ultimately overcome the inherent challenges in faithfully eradicating established tumors. Our Td pre-conditioning platform in the context of DC vaccination also elicited superior anti-tumor responses compared to controls receiving DC vaccines without Td pre-conditioning. In our clinical trial (Pro00003877 ATTAC), patients with newly-diagnosed GBM who were administered the

Td skin pre-conditioning before DC vaccination revealed significantly longer PFS and OS compared to the control cohort receiving unpulsed DCs. In evaluating the relationship between DC migration and clinical responses, we observed a positive association between levels of DC migration and survival. In addition, based on our preliminary data that Td vaccine site pre-conditioning enhances the immunogenicity of PEP-CMV in HLA-A2 transgenic mice, all patients will also receive a Td vaccine site pre-conditioning in the RIGHT groin and the following day receive the PEP-CMV vaccine.

[figure not shown]
In this protocol, the goal is to determine the safety of PEP-CMV vaccine with adjuvant TMZ, and what TMZ regimen produces the highest number of T cells that specifically secrete IFN γ by ELISPOT in response to PEP-CMV component A.

